Acute Effects of Endurance Exercise with Moderate and High Intensity on Breast Milk Composition Among Women with Overweight/Obesity

Acronym: YT

NCT number: NCT05745922

Document date: 07. September 2025

Statistical Analysis Plan

Study design: Randomized crossover study

Aim: Determine the effect of moderate-intensity continuous training and high-intensity interval training on human milk concentrations of metabolites, lipids, cytokines, hormones and miRNAs in lactating women with overweight/obesity.

Overview:

- Up to N=30 women with $\text{BMI} > 25 \text{ kg/m}^2$
- Each participant goes through three conditions in random order (six possible sequences) and has milk sampled at four time points per condition (one pre-condition and three post-condition).
- Washout period: 1 week between conditions
- The samples are analysed for a range of outcome variables within different molecular data ('omics') categories.

Conditions:

- C1: No exercise, resting in the lab
C2: Moderate-intensity continuous training
C3: High-intensity interval training

Time points:

- T1: 7 am (pre-condition)
T2: 11 am (immediately after condition)
T3: 12 am (1-hour post-condition)
T4: 15 am (4 hours post-condition)

Pre-planned outcome groups measured in human milk:

- Targeted NMR metabolomics (GCF)
Metabolomics + lipidomics profile panels (Metabolon)
Cytokines (Olink)
Hormones (insulin, ghrelin, leptin, adiponectin, IGF-1)
miRNA (GCF)

Statistical analysis plan

For each outcome category, the primary objective is to evaluate the effect of conditions C2 and C3 on the outcome variables at time points T2, T3, and T4, using condition C1 and time point T1 as references. Outcomes measured in all participants will be analysed according to the intention-to-treat principle, whereas outcomes measured only in participants who followed the protocol perfectly will be analysed according to the per-protocol principle. The decision whether to include all samples or only those from participants who complied with the protocol will depend on the costs of including the extra (non-compliant) samples for each outcome group.

We will perform the following six analysis steps for all outcome groups:

1) Data preparation (batch adjustment, log transformation, imputation)

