- If needed, the outcome data will be batch adjusted, imputed (e.g. using the R package *zCompositions*), and log transformed appropriately before analysis. Adjustments and transformations will depend on whether the data is already normally distributed, and if it is required for the method in question.
- The metabolomics data from Metabolon already comes in a log-transformed, batch-normalized version where missing values (below the detection limit) are imputed to the observed minimum for that metabolite after batch normalization. These will be used in all analyses.

2) Principal component analysis (PCA)

- We will use PCA to detect outliers and identify global structures/important features by capturing the maximum variance in the dataset, and test if the data separates according to the conditions in an unsupervised setting.
- We will identify the number of PCs that explain 95% of the variation in the data at baseline, for use in multiple testing adjustment.

3) Linear mixed model (LMM) analyses:

- We will use LMM analyses to evaluate the effects of each condition and time point on all outcome variables:
- We will analyse the effects of time and time-condition interaction as fixed effects, and participant ID as a random intercept (Eq 1). The analysis will be reference coded, with C1 (no exercise) and T1 (morning) as reference points. We will not adjust for or subtract baseline values in the model.

Eq. 1: $\text{value} \sim \text{time} + \text{time:condition} + (1|\text{id})$

- We will run the LMM analyses using e.g. the lme4 R package, and estimate p-values using the Satterthwaite method, e.g., as implemented in the lmerTests R package.
- Multiple testing correction: We will use a multiple testing corrected p-value threshold determined by dividing the alpha level (0.05) by the number of PCs explaining 95% of the variation in the outcome data at baseline.
- For variables passing the multiple testing corrected p-value cut-off, we will test for potential carry-over effects by adjusting for sequence (Eq. 2) in sensitivity analysis:

Eq. 2: response matrix ~ time + time:condition + sequence + sequence:condition + time:sequencec:condition + (1|id)

4) Repeated Measures (RM)-ASCA+

- We will use RM-ASCA+ to evaluate the overall effect of each condition and time point on each outcome data category. We will model all variables within the same data category together in a multiple-response variable analysis.

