- We will analyse both the combined and separate effects of time and time-condition interaction as fixed effects, and participant ID as a random intercept (Eq 3). The analysis will be reference coded, with C1 (No exercise) and T1 (morning) as reference points. We will not adjust for or subtract baseline values in the model.

Eq. 3: response matrix ~ time + time:condition + (1|id)

- Each variable will be scaled by the standard deviation of the baseline (morning) samples across conditions.
- We will use cluster bootstrapping with 1000 iterations to validate the findings and generate confidence intervals.

The results from the LMM and RM-ASCA+ analyses will guide follow-up analyses using additional machine learning models (PLS-DA, t-SNE).

5) Partial Least Squares Discriminant Analysis (PLS-DA)

- Supervised machine learning approach to analyse differences between the conditions. We will provide the model with a response matrix specifying the conditions, and the model will maximize separation between the conditions. The

method works well with small datasets and multiclass scenarios (here: multiple conditions).

- We will use PLS-DA for feature selection/to explore global structures in the data or find variables that are especially important for one time/condition compared to another. The LMM and RM-ASCA+ analyses will guide the selection of conditions/time points for comparison.
- We will perform cross-validation and permutation testing with 1000 repetitions.

6) T-Distributed Stochastic Neighbour Embedding (t-SNE)

- We will use t-SNE in an exploratory analysis to look for clusters of variables by preserving local relationships (pairwise similarities between data points, clusters).

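### The carry-over check in SAP Eq. 2 does not isolate carry-over: its sequence terms mix it with any visit trend, and no separating contrast is named

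*SAP*

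**What the plan says.** The Overview of the SAP sets out the design: "Each participant goes through three conditions in random order (six possible sequences", with four milk samples per condition and a week between conditions. The primary objective is the effect of C2 and C3 "on the outcome variables at time points T2, T3, and T4, using condition C1 and time point T1 as references".

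The main model (step 3, Eq. 1) has time and time:condition as fixed effects and "participant ID as a random intercept (Eq 1". On coding: "The analysis will be reference coded, with C1 (no exercise) and T1 (morning) as reference points". Eq. 3, for RM-ASCA+ in step 4, has the same right-hand side: "response matrix ~ time + time:condition + (1|id".

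The carry-over check comes at the end of step 3. It applies "For variables passing the multiple testing corrected p-value cut-off", and there "we will test for potential carry-over effects by adjusting for sequence (Eq. 2) in sensitivity analysis". Eq. 2 reads "response matrix ~ time + time:condition + sequence + sequence:condition + time:sequencec:condition + (1|id".

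The SAP does not say which term or contrast of Eq. 2 represents carry-over, which threshold applies, what the reference sequence is, or what follows from a positive result. Neither document gives a visit (period) term.

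**The concern.** Carry-over depends on the condition at the preceding visit. Sequence labels the whole order, so adjusting for sequence is not in itself a test of carry-over. The visits are a week apart between 5 and 12 weeks postpartum (protocol, Participants), so milk composition may drift from visit to visit for reasons unrelated to exercise. If the check responds to that drift, a sound result may be reported as contaminated by carry-over. The reader also needs the exercise effect after allowing for carry-over, and the SAP does not say which quantity from Eq. 2 that is.

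**Working it through.** **Inputs.** From the documents: 3 conditions, 6 sequences, 4 samples per visit; at least 20 complete women (protocol, Participants) and up to 30 (SAP, Overview); Eqs. 1 to 3. That is 20/6 = 3.3 to 30/6 = 5 women per sequence. The documents give no trend, carry-over size, variance or number of principal components. Those are assumptions below, in units of the residual SD of one sample. The plan states no figure to reproduce.

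**1. What the equations contain (no assumed sizes).** Fixed-effect ranks:

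| Model | Rank |
|---|---|
| Eqs. 1 and 3 | 12 |
| Eq. 1 + period | 14 |
| Eq. 1 + time:period + time:previous | 28 |
| Eq. 2 | 72 = 6 × 3 × 4 |
| Eq. 2 + time:period + time:previous | 72 |

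Sequence and condition together fix both the visit number and the preceding condition, so both effects already lie inside Eq. 2. At visit level, sequence + condition has rank 8, adding period gives 10, adding first-order carry-over gives 12, and the full set is 18. The sequence:condition term has (6−1)(3−1) = 10 df: 2 for period, 2 for carry-over and 6 for neither.

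**2. Visit trend, no carry-over.** For the 10-df test with equal sequences, the noncentrality is N × 4 × Σ(visit − mean)² × trend², where the sum is 1 + 0 + 1 = 2.
- N=30, trend 0.2: 30 × 4 × 2 × 0.04 = 9.6. Residual df are 360 − 72 − 24 = 264. Rejection at alpha 0.05 is 50%.
- N=20, sequences as equal as possible: noncentrality 6.35, residual df 240 − 72 − 14 = 154, rejection 32%.
- At trend 0.1 the rates are 10 to 13%; at 0.3 they are 70 to 91%.
- At 0.05 divided by 5 to 40 components, trend 0.2: 13 to 4% (N=20) and 27 to 10% (N=30).

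**3. Real carry-over of 0.5 after C3 at all samples, N=30.** C3 precedes another visit in 4 of 6 sequences, so 20 women have one raised visit. The within-woman sum of squares is 20 × 4 × 0.25 × 2/3 = 13.33. Mean carry-over into C1, C2 and C3 is 1/6, 1/6 and 0, so condition removes 120 × 1/54 = 2.22 and leaves 11.11 for the 10-df test: power 0.58. The visit means are 0, 1/6 and 1/6, so period removes another 2.22 and leaves 8.89 for the 2-df test of preceding condition: power 0.76. At N=20 the powers are 0.37 and 0.55.

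**4. Other readings of Eq. 2.** No test is named, so several are possible (N=20 to 30, alpha 0.05):

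| Test | Rejects: trend 0.2, no carry-over | Power: carry-over 0.5 |
|---|---|---|
| sequence:condition, all times, 10 df | 32–50% | 0.37–0.58 |
| sequence:condition at T1, 10 df | 10–13% | 0.11–0.15 |
| all sequence interactions, 55 df | 13–20% | 0.14–0.23 |
| sequence main effect, 5 df | 5% | 0.05–0.06 |
| previous condition with period, 2 df | 5% | 0.55–0.76 |

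**5. The unit matters.** If each visit supplies one value with SD 1, the 10-df test rejects in 11 to 17% at trend 0.25 and 35 to 66% at trend 0.5 (N=18 to 30). Its power for carry-over of 0.5 is then 0.09 to 0.13. The direction is the same.

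**6. Exercise effect.** C3 comes directly before C1 in 2 of 6 sequences and never before itself. Averaging Eq. 2 equally over sequences therefore leaves −1/3 of the carry-over in the same-time C3−C1 difference: −0.5/3 = −0.167. Read as reference-coded coefficients instead, time:condition describes one unspecified sequence, with a standard error 2.2 to 2.6 times that of Eq. 1.

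**7. Correlation within a visit.** With visit variance of 0.1, 0.25 or 0.5 of residual variance, no trend and no carry-over, the 10-df test under (1|id) rejects in 16–17%, about 35% and 57–58%. The 2-df test under (1|id) rejects in 10%, 16–17% and 25%; with a participant-by-visit intercept it rejects in 5%.

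**8. Period missing from Eqs. 1 and 3.** Randomised order gives no bias on average. The standard error rises by √(1 + (2/3) × trend²) = 1.013 to 1.030 at trends 0.2 to 0.3. With near-equal sequences the worst C3−C1 visit imbalance is 0.15 (N=20), 0.19 (N=21) or 0 (N=24, 30) of the per-visit trend. Under simple randomisation, an assumption since the documents say only that order is random, its SD is 0.32 (N=20) to 0.26 (N=30).

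**The case against.** The strongest reply is that a saturated model leaves nothing out. That is true: a fixed weighting of Eq. 2's sequence-by-condition means recovers the C3 effect free of additive period and first-order carry-over, at 1.25 times the variance (SE × 1.12). With C1-C2-C3 as reference sequence, the C2−C1 coefficients contain no exercise carry-over, though they are noisy and confounded with visit. A reader might infer that Eq. 2 can give no carry-over-adjusted effect. The equations do not support that; the accurate statement is that the SAP names no such contrast.

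Second, the rejection rates rest on an assumed trend, joint F-tests that the SAP does not specify, and alpha 0.05. This stands, so the rates are illustrations. The ranks do not depend on it.

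Third, within-visit correlation should not be charged to Eqs. 1 to 3 alike. Only Eq. 2 has the sequence:condition test in question, and step 4 uses a cluster bootstrap for Eq. 3. This stands.

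Fourth, checking only variables that passed the cut-off is a defensible use of a robustness check on positive results. It does mean that carry-over masking an effect goes unexamined, but that is a choice and not an error.

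Finally, this is a sensitivity analysis in an exploratory study, and no rule drops a result because of Eq. 2. That limits the consequence. It does not make the check interpretable.

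**Conclusion.** The point holds. As specified, a signal from Eq. 2 cannot be read as carry-over, and under some readings the absence of a signal says almost nothing. The confounding follows from the equations alone. Its size depends on a trend that the documents do not give: across trends of 0.1 to 0.3, the 10-df test at alpha 0.05 gives a false signal in 10 to 91%. The 2-df comparison assumes first-order carry-over that does not depend on the condition that follows.

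A reader might infer that carry-over is present or that the exercise effects are biased. The documents do not support this. They give no carry-over size, they provide a week of washout, and the protocol (Human Milk Lipids) regards the effect on one lipokine as transient. Any bias would also depend on timing: in the change from T1 it cancels if carry-over is equal at all four samples, and it remains in full if carry-over acts only after T1.

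The missing period term in Eqs. 1 and 3 is minor. The check should be rewritten before analysis; the main model needs only a small addition.

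**What to change.** 1. Replace Eq. 2 with `value ~ time + time:condition + time:period + time:previous + (1|id) + (1|id:visit)`. Code previous condition as two indicators (C2 or C3 at the preceding visit), both 0 at visit 1.
2. Name the 2-df test of previous condition, averaged over the four times, as the carry-over test.
3. Report this model's condition effects whatever the test shows, next to the same model without the previous-condition terms and with the same random effects, so that the difference reflects carry-over adjustment alone. Give them as same-time differences from C1 and as changes from T1.
4. Add period (visit 1, 2, 3) as a fixed factor to Eqs. 1 and 3.

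Running the check on all variables is optional.

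**Cost.** SAP wording only; visit order is known from the randomised sequence. Period in Eqs. 1 and 3 takes 2 df and leaves the standard error essentially unchanged. In the sensitivity model the standard error of the time-specific condition effects rises by about 10%. If visit variance is 0.25 to 0.5 of residual variance, the reported same-time standard errors can be about 13 to 16% above those of Eq. 1, partly because Eq. 1 ignores that variance.

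The carry-over test has limited power. For 0.5 SD at all samples and alpha 0.05, with the visit intercept, it is 0.52 to 0.74 without visit variance and 0.28 to 0.43 with visit variance 0.25. The SAP should say that a non-significant result does not exclude carry-over.

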Exercise represents a major challenge to whole-body homeostasis and affects multiple cells, tissues, and organs in response to the increased metabolic activity of contracting skeletal muscles.¹⁷ It was recently shown that there is a dramatic shift in > 80% of annotated metabolites in the circulating metabolome in response to a single endurance-type exercise session of just 12 minutes, with beneficial alterations in metabolites representing key metabolic pathways central to obesity, insulin resistance, and inflammation.²⁶ Such alterations can help explain the broad exercise-induced benefits on cardiovascular and metabolic health.

Apart from the scarce evidence on exercise-induced adaptations in breastmilk, there is very little knowledge about how maternal exercise training affects milk composition. Women are recommended to be physically active after childbirth, but the emphasis is on maternal weight control and fitness. Current guidelines for exercise in lactating women are sparse. The most recent recommendations from the American College of Obstetricians and Gynecologists⁴⁸ merely states that “*regular aerobic exercise in lactating women has been shown to improve maternal cardiovascular fitness without affecting milk production, composition, or infant growth.*” These recommendations are based on observational studies^{49,50} and one small RCT⁵¹ from the 1990s, before today’s

advancements in various ‘omics’ technologies and the application of computational and systems biology approaches. Furthermore, no prior studies have investigated the role of exercise intensity for adaptations in breastmilk composition. There is now substantial evidence for superior effects of high-intensity exercise, as compared to moderate-intensity exercise, in a range of clinically relevant health outcomes.^{52,53}

Aim and hypotheses

The overall aim of this project is to determine the acute effect of maternal exercise on breastmilk composition. We will also compare the effects of moderate versus high intensity exercise on breastmilk composition. Our hypothesis is that: Exercise will induce substantial changes in breastmilk composition after a single endurance exercise session, with greater effects of high-intensity exercise than of moderate intensity exercise.

Methods

Participants

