We will include 20-25 women with $\text{BMI} > 25 \text{ kg/m}^2$ who are exclusively breastfeeding a singleton term infant. Participants will provide a written informed consent. The assessments will be completed between 5 and 12 weeks postpartum, with the first assessment 5-9 weeks postpartum. No formal power calculation is possible for the acute study due to the exploratory nature of the research. We will continue including participants until we have complete data for all three sets of conditions for at least 20 participants. The crossover design of this study will decrease the interindividual variation in the statistical analysis. The women will serve as their own controls, which will remove any interindividual biological variance in breastmilk.

Experimental design

This will be a randomised cross-over study, in which all participants undergo three different conditions, in random order (Fig. 2):

- 1) Moderate intensity exercise; 48 min at $\sim 70\%$ of heart rate maximum
- 2) High-intensity exercise; 4 x 4 min at 90-95% of heart rate maximum
- 3) No exercise. Resting in the lab.

[figure not shown]

Fig. 2. Exercise will take place at 1000h, and breastmilk will be sampled at 0 h (immediately after exercise), + 1 h and + 4 h after exercise/no exercise. Dietary intake will be standardised on the day before and on the day of the experiment. Moderate intensity exercise (A), High intensity exercise (B) and No exercise (C) will be separated by one week and will be undertaken in random order.

Participants will walk or run on a treadmill during both exercise conditions. *Inclusion criteria:* Besteen 5+6 and 8+6 weeks postpartum at the first condition in the study, exclusively breastfeeding a term infant. *Exclusion criteria:* Known cardiovascular disease, type 1 or 2 diabetes.

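### The only check on RM-ASCA+ is a bootstrap that shows how stable a pattern is, not whether exercise has an effect; the step needs a within-woman randomisation test

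*SAP*

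**What the plan says.** RM-ASCA+ is step 4 of the six steps that the SAP applies to every outcome group. Its purpose is stated as follows: "We will use RM-ASCA+ to evaluate the overall effect of each condition and time point on each outcome data category". The model (Eq. 3) has fixed effects for time and for time by condition and a random intercept per woman, with C1 (no exercise) and T1 (morning) as references. On output, the SAP says "We will analyse both the combined and separate effects of time and time-condition interaction as fixed effects"; on scaling, "Each variable will be scaled by the standard deviation of the baseline (morning) samples across conditions". The check on the results is one sentence: "We will use cluster bootstrapping with 1000 iterations to validate the findings and generate confidence intervals".

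Step 4 gives no null reference, significance level or multiplicity rule. It does not say which pattern of scores counts as an effect, whether the effect matrix is centred before the component analysis, or how components from bootstrap samples are aligned with those from the full data.

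Other steps differ. Step 3 (LMM) tests each variable at 0.05 divided by a number of principal components. Step 5 (PLS-DA) has cross-validation and 1000 permutations, on comparisons chosen in the light of the LMM and RM-ASCA+ results. The protocol's hypothesis, under Aim and hypotheses, concerns composition as a whole: "Exercise will induce substantial changes in breastmilk composition after a single endurance exercise session".

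**The concern.** RM-ASCA+ runs a component analysis on the estimated condition effects. The first component is by construction the direction in which those estimates, noise included, lie furthest from the origin. Resampling women gives replicates that scatter around that estimate, so the score intervals are centred on a value already pushed away from C1. An interval that excludes C1 shows that the fitted pattern recurs when women are resampled. It does not show that the pattern would be unusual if exercise did nothing.

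Because the SAP assigns the bootstrap to validate the findings, such an interval is likely to be reported as a validated change in milk composition for that category. The same result also helps choose the conditions and time points that go into PLS-DA, whose permutation test cannot undo a selection made on the same data.

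**Working it through.** The documents give no error rate for this step, so there is no figure to reproduce. The check is the behaviour of the planned procedure when there is no condition effect.

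**Inputs from the documents.** Three conditions, four time points, six sequences. The protocol recruits until there is "complete data for all three sets of conditions for at least 20 participants"; the SAP overview has "Up to N=30 women with" BMI above 25. Six contrasts: C2 and C3 against C1 at T2, T3 and T4. Panel sizes: 5 hormones (SAP), 27 cytokines (protocol panel; the SAP names Olink without a count), more than 1000 metabolites (protocol).

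**Assumptions.** Variance components, correlation between variables, test-day variation, alignment method and reading rule come from no document. The main reading was the separate time-by-condition matrix, uncentred, first component, bootstrap components rotated to the originals, 95% percentile intervals.

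**Mechanism.** With balanced data the estimated effect for condition c, time t and variable j is the difference of cell means, b(c,t,j) = mean(c,t,j) − mean(C1,t,j). Let E be the matrix of these effects. The first component v maximises the sum over rows of (E·v)². With no effect, E is pure noise, and v is chosen to make the projections of that noise large. A bootstrap replicate is E plus further noise, so it is centred on E and not on zero.

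**Benchmark.** Six independent, correct 95% intervals would give 1 − 0.95⁶ = 1 − 0.735 = 26.5% with at least one exclusion. In simulation, a direction fixed in advance gave about 20–43%.

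**Null datasets with at least one of six intervals excluding C1**

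| Variables | Setting A: 20 women, between-woman variance 4 × residual, half the variance shared | Setting B: 20 / 30 women, with test-day variation |
|---|---|---|
| 5 | 48% | correlated 47% / 51%; uncorrelated 60% / 59% |
| 27 | 52–61% | correlated 83% / 80%; uncorrelated 100% / 100% |
| 200 | 59–75% | correlated 100% / 98% |
| 1000 | 52–84% (25 datasets) | correlated 100% / 100% |

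Ranges in setting A cover test-day variance of 0 to 0.5 × residual. Two further sets of runs with 20 women gave 52–100% and 56–95%. Monte Carlo error in setting B is about 3–4 points for 5 and 27 variables, and larger for 200 and 1000.

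**Per interval, against 5% intended.** Setting A gave 11% (5 variables), 13–18% (27) and 15–27% (200); another set gave 13–44%. Setting B went higher with large or uncorrelated panels (82% for 200 correlated and 94% for 27 uncorrelated variables, 30 women). Test-day variation matters: for 27 correlated variables and 25 women, the per-interval rate rose from 11% with none to 71% at the largest value tried.

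**Other readings the SAP leaves open**

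- Combined time plus time-by-condition plot: 0–19% if read by overlap of intervals, 16–95% if read by an interval on the difference.
- Centred matrix read by overlap: 21% (5 variables) and 29% (27) in setting B with 25 women; 23–27%, 31–35% and 35–51% (5, 27 and 200 variables) in another set.
- Centred matrix read by an interval on the difference: 41% (5) and 55% (27).
- Sign alignment only: 17% (5) and 51% (27).

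**Randomisation test.** Re-assigning condition labels within each woman, with the condition-effect sum of squares as statistic, rejected in 82 of 1600 null datasets in setting B (82/1600 = 5.1%), in 4.5–6.5% in setting A, and in 6.6% (of 1200 datasets) and 2.5–7.5% in the other sets.

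**Pairwise comparisons.** Re-drawing all three days tests only the global null. Used for C2 against C1, it lets C3 days into the reference distribution. With 27 variables and a C2 shift of 0.4 residual SD, power for C2 against C1 was 82% with no C3 effect, 56% with a C3 shift of 1.0 and 8% with 1.5. Swapping only the C1 and C2 days kept 82–88%. A second check gave a fall from 99% to 7%, against 96–98% with the swap.

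**The case against.** The strongest reply has four parts.

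First, the false-finding rate depends on choices that the SAP does not make. A reader might infer that half or more of null datasets will show an exercise effect whatever is done. The documents do not support that: they state no rule under which any one of six intervals decides, and some readings they permit give far lower rates. This stands, and the rate must be stated as conditional. A procedure whose error rate can run from near 0 to 100% through unstated choices still lacks a test.

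Second, part of the excess comes from six uncorrected looks and not from component fitting. This also stands. With Bonferroni-width intervals the any-of-six rate fell from 46–52% to 17–20% (5 variables) and from 51–79% to 21–37% (27 variables). That remains well above 5%, so component fitting accounts for a real share.

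Third, a reader might infer that RM-ASCA+ is the only analysis of a whole category. It is not. Step 2 looks for separation by condition, though it names no test, and step 5 fits whole categories with permutation, though only after comparisons have been selected. The SAP's primary objective concerns the outcome variables, and step 3 tests those against a corrected threshold without passing through RM-ASCA+.

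Fourth, the protocol calls the research exploratory, and no document says that a bootstrap interval will settle a confirmatory claim. That limits the severity. It does not remove the problem: the protocol uses the word to explain the missing power calculation, and it also states a directional hypothesis about composition.

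**Conclusion.** The concern holds for RM-ASCA+ as a test of an overall condition effect. Step 4 relies on bootstrap intervals alone, and these cannot separate a stable pattern from a real effect when the components come from the same estimates. The mechanism is certain; its size is conditional. For the separate time-by-condition effect on the first component with rotated bootstrap components, false exclusion was roughly 11–44% per interval in most settings and about 47–100% for any of six, against about 20–43% for a direction fixed in advance. These figures rest on assumed variances and correlations, complete balanced data and an assumed reading rule.

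A reader should not conclude that the trial's main inference fails: the per-variable LMM results are unaffected. This is a should-fix point.

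**What to change.** Add one paragraph to SAP step 4.

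- Keep the cluster bootstrap, and state that its intervals describe the stability of scores and loadings and will not be read as tests.
- Base any claim of an overall condition effect in an outcome category on a within-woman randomisation test with at least 1000 re-draws, keeping the four samples of each test day together. The statistic is the sum of squares of the T2–T4 condition effects from Eq. 3. State the significance level.
- For the global test, re-draw the order of all three days within each woman from the six sequences.
- For C2 against C1 and for C3 against C1, swap only the two days being compared and leave the third in place.
- State the centring and alignment used for the plots, so that the descriptive intervals can be interpreted.

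The cost is that paragraph and computing time; data collection does not change. Fewer categories may show a validated effect.

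### PLS-DA comparisons are guided by LMM and RM-ASCA+ results from the same samples, and the permutation test makes no stated allowance for that choice

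*SAP*

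**What the plan says.** The SAP applies six analysis steps to every outcome group. Steps 3 (LMM) and 4 (RM-ASCA+) estimate the effects of time and of condition by time. The text closing step 4 says that their results will steer the follow-up work with PLS-DA and t-SNE.

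Step 5 gives PLS-DA the purpose of selecting features, exploring overall structure, or picking out variables that matter more in one time or condition than in another. It then says how the comparisons are found: "The LMM and RM-ASCA+ analyses will guide the selection of conditions/time points for comparison". The validation is then one line: "We will perform cross-validation and permutation testing with 1000 repetitions".

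The SAP does not list the PLS-DA comparisons, state a selection rule, set samples aside, say whether labels are shuffled within or across women, or say whether the selection is repeated in each permutation. It gives no significance level for PLS-DA. Its one multiplicity rule, in step 3, is a threshold found by "dividing the alpha level (0.05) by the number of PCs explaining 95% of the variation in the outcome data at baseline". That rule belongs to the LMM and counts principal components, not conditions or time points.

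**The concern.** A permutation p-value is valid when the permuted datasets go through the same procedure as the real one. Here the real data first help to decide which comparison is made. If labels are then shuffled for that comparison alone, the reference distribution is that of a comparison taken without looking, while the observed statistic comes from one favoured by the data. The p-value is then too small on average.

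Cross-validation does not remove this, because the women in every fold contributed to the choice. Keeping all samples of a woman together does not remove it either: that deals with the pairing, not with the selection. The same argument applies in kind to the cross-validated accuracy of a chosen comparison, but no figure for that was computed.

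At stake is how a small permutation p-value from step 5 is read. It would partly restate what steps 3 and 4 had already shown in the same samples. Because the six steps apply to all outcome groups, the question arises in each.

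**Working it through.** The documents give no error rate, alpha or power for PLS-DA, so there is no stated figure to reproduce.

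**Inputs from the documents**
- Candidate comparisons: the primary objective in the SAP is to "evaluate the effect of conditions C2 and C3 on the outcome variables at time points T2, T3, and T4", with C1 as reference. That is 2 conditions × 3 times = 6. Adding C3 against C2, which the intensity hypothesis in the Protocol (Aim and hypotheses) makes natural, gives 3 × 3 = 9. A three-class model at one chosen post-condition time has 3 candidates.
- Women: "Up to N=30 women" (SAP, Overview) and "We will include 20-25 women" (Protocol, Participants). The simulations used 20 to 30.
- Structure: 3 conditions × 4 times in each woman, so the data are paired.

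**Assumptions that the documents do not give**
- p ≤ 0.05 counts as positive, and the single largest contrast is taken forward.
- One-component PLS-DA, with 5-fold cross-validation by woman.
- 5 to 200 correlated variables; share of variance between women 0–0.7 and between visits 0–0.5.
- 99–199 permutations and 400–2000 null datasets per setting.

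**Benchmark.** For k independent tests at 5%, the chance of at least one false positive is 1 − 0.95^k:
- k = 3: 1 − 0.857 = 14.3%
- k = 6: 1 − 0.735 = 26.5%
- k = 9: 1 − 0.630 = 37.0%

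The real contrasts share samples, and the statistic used to select is not the one used to test. Somewhat lower rates are therefore expected when the best contrast is simply picked.

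**Simulated rate of p ≤ 0.05 with no true effect**

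| Reading | Rate |
|---|---|
| One contrast fixed in advance, labels permuted within woman | 4.0–6.5% |
| Largest of 6 pairwise contrasts, within woman | 15–23% |
| Largest of 9 pairwise contrasts, within woman | 19–26% |
| Three classes at the best of 3 times, within woman (in-sample between-condition statistic) | 9–13% |
| PLS-DA run only after an LMM hit, within woman (rate among datasets with a hit) | 15–36% |
| Largest of 6, labels shuffled ignoring woman, between-woman share 0.3–0.7 | 5–18% |
| Same shuffle, between-woman share 0 | 32% |

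The shuffle that ignores woman is not a correct test to begin with. Without any selection it gave 0.7–4% at shares of 0.3–0.7, and 8.5% at a share of 0. Its low figures therefore reflect a conservative test, not an absence of selection bias. Combining that shuffle with an LMM hit widened the range to about 3–39%.

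Two further simulations of the six-contrast, within-woman case agree. With 20 women, 27–1000 variables, leave-one-woman-out validation and sign-flips, the rate was 4.4–5.4% for a contrast fixed in advance and 19–24% for the selected one. With 20–25 women and sign-flips, it was 3–6% and 18–26%.

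**Does the selection cause it?** Condition labels were permuted within woman, the largest of the six contrasts was re-selected in each permutation, and PLS-DA was refitted. The rate fell to 5.2% (20 women) and 6.2% (25 women), with 400 datasets each. The Monte Carlo standard error is √(0.05 × 0.95 / 400) = 0.011, so both agree with 5%.

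**The case against.** The strongest reply is that PLS-DA carries no confirmatory weight here. The SAP openly calls it follow-up work guided by earlier results and gives its purpose as selecting features and exploring structure. Condition and time effects are evaluated by the LMM and RM-ASCA+, and the Protocol (Participants) calls the research exploratory. No decision is tied to a PLS-DA p-value. This stands, and it limits the consequence. It does not remove the point, because the SAP also presents PLS-DA as a way to analyse differences between conditions and attaches a permutation test, which yields a p-value that readers will take as validation.

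The second reply is that the size is not fixed by the plan. The word used is guide, which could mean running every comparison that the earlier steps flag rather than the largest one. Step 5 recommends PLS-DA for several classes at once, which supports a three-class model with fewer candidates. The permutation unit is not stated. All of this stands, so the size must be given as a range tied to assumptions. In the other direction, the SAP also allows comparisons between times, which would add candidates; that case was not examined.

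A reader might also infer that PLS-DA will be presented as independent confirmation of the LMM and RM-ASCA+. The documents do not say so. The risk lies in how a p-value would be read, not in a stated claim.

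**Conclusion.** The point holds in a limited form. As written, step 5 lets results from the same samples guide the choice of comparison and then tests that comparison by permutation with no stated allowance for the choice. A permutation p-value obtained in this way is optimistic.

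A reader might go further and conclude that this SAP runs a 5% test at about 20%. The documents do not support that as a property of the plan. The figure needs a 5% level that the SAP does not set for PLS-DA, six pairwise candidates, automatic choice of the largest, and within-woman permutation. Under those four assumptions, about 15–25% is a fair statement. The spread across the other readings shows that the direction is better established than the size.

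Nor do the documents support the inference that the main results are compromised. The selection runs from the LMM and RM-ASCA+ to PLS-DA and not back, so their estimates and p-values are unaffected by this point.

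**What to change.** Amend step 5 of the SAP in one of three ways, before the PLS-DA is run.

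1. List the comparisons now: C2 against C1, C3 against C1 and, given the intensity hypothesis, C3 against C2, each at T2, T3 and T4 (nine in all). A three-class model at each of the three times would also serve. Run all of them whatever steps 3 and 4 show. Permute condition labels within woman, moving all samples of a visit together, and refer each result to the permutation distribution of the maximum over the list.
2. Keep the guided choice, but write it as an explicit rule and repeat that rule inside every within-woman permutation.
3. Keep the guided choice and report the chosen comparisons as description, with no p-value and no claim that they confirm the LMM or RM-ASCA+ results.

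Under options 1 and 2, the SAP should also state the permutation unit and the significance level, since the size of the problem depends on both.

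The cost is a few lines of SAP text and, for option 1, up to nine automated PLS-DA runs per outcome group. No new samples or assays are needed. The adjusted p-values will be less favourable. Option 3 adds no computing and fits the exploratory purpose that the SAP already states.
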